## **METHODOLOGY**

### Inclusion criteria:

- Aged 12 to 21 years;
- Planned for removable retention with Essix-type vacuum-formed retainers;
- Fit and well and on no medication;
- In the permanent dentition.

### The exclusion criteria:

- Inability to access or peruse electronic mail;
- Cleft lip and palate and other craniofacial anomalies.

## **Study Design / Plan – Study Visits**

Subjects will be recruited for inclusion at a routine adjustment appointment prior to planned removal of the appliances in the Orthodontic Department at Institute of Dentistry, Barts and The London School of Medicine and Dentistry, UK. Following removal of the appliances, consenting participants will be randomly allocated to one of two groups by computer-generated random allocation. Allocation will be concealed from the treating clinician using of an opaque sealed envelope system. Study models will be available for all participants following removal of the appliances (T1).

Participants in both groups will have follow-up scheduled for 3 (T2), 6 (T3) and 12 (T4) months following removal of the appliances. All participants will be instructed to wear vacuum-formed (Essix-type) retainers on a full-time basis for 6 months, followed by night-time wear for a further 6 months (Gill et al., 2007). A Thera-Mon™ micro-electronic timer will be integrated within the upper Essix-type retainer. All participants will be given standard advice at each recall visit. If any patient from both groups fails to attend their routine retainer check visit, another appointment will be arranged and posted through Royal Mail.

Participants in the intervention group will receive tailored electronic reminders. The frequency and content of the reminders will be informed by the qualitative findings of an ongoing trial, but are likely to include an intra-oral photograph taken pre-treatment and following removal of the active appliances, instructions on the necessary duration of retention, advice on maintenance of retainers, departmental details, advice on appropriate management for appliance breakages, and delineation of the implication of suboptimal retainer wear. Participants in the control group will not receive additional reminders.

Treating clinicians will be kept blind to the study group.

All patients failing an appointment will be sent another. Those wishing to withdraw from the trial may do so at any point without affecting continuing care with records taken at the point of withdrawal from the study with data analysis on an intention to treat basis.

One-to-one interviews will be undertaken by the researcher on subset of participants in confidential, non-clinical areas at the Institute of Dentistry. The interviews will be based on a topic guide, which will draw on existing literature and professional experiences. This will facilitate discussion based around the aims of the research. Themes to be explored are likely to be patients' acceptance and experience of electronic reminders. Discussions will be recorded digitally and transcribed verbatim. Transcripts will be entered in NVivo 10 TM qualitative data analysis software (QSR International) and anonymised for analysis.

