## TRIAL OBJECTIVES

**Primary /Secondary Objectives to be outlined as defined by the Primary/Secondary Endpoints which are also to be listed here.**

The primary objective is to explore the effect of electronic reminders on compliance with orthodontic retention.

The secondary objectives are to assess the subjective levels of retainer wear and to measure upper/lower anterior irregularity and transverse dimensional changes during the retention phase. We also aim to explore patients' experience with electronic reminders in a related qualitative element.

- Primary Endpoint

Objective level of compliance with retainer wear at 6 months (T3) of orthodontic retention.

- Secondary Endpoints

Objective level of compliance with retainer wear at 3 months (T2) and 12 months (T4) of orthodontic retention.

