### **Study Scheme Diagram**

To reinforce the above and which demonstrates the life cycle of the study in a schematic form (see example below)

Please refer to figure 1.

[figure not shown]

Figure 1. CONSORT chart showing the flow of participants through each stage of the trial

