## STUDY PROCEDURES

Participants will be recruited by treating clinicians at Institute of Dentistry, Barts and The London School of Medicine and Dentistry. Potentially eligible participants will be given an information sheet detailing the study and its objectives at the visit prior to removal of their fixed appliances. Participants agreeing to be involved will be asked to sign a consent form for inclusion in the study at the following visit. Patients under 16-18 years can consent for themselves only if they were deemed mature to make a decision, this will be decided by the CI and PI. Otherwise, the parent will be asked to consent for their child.

Following removal of the appliances, consenting participants will be randomly allocated to one of two groups by computer-generated random allocation. Allocation will be concealed from the treating clinician using of an opaque sealed envelope system. Standard orthodontic study models will be available for all participants following removal of the appliances (T1).

Participants will then be reviewed at 3, 6 and 12 months for regular retainer checks and collection of records i.e. study models and microsensor readings.

One-to-one interviews will be undertaken in a confidential non-clinical areas. Interviews will continue until data saturation has been achieved characterized by a lack of new emergent themes.

All documents including models will be securely held in a locked office, photos will also be stored on an encrypted trust computer.

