### Sample Size Calculation

Based on previous research (Tsimos et al., 2014) alluding to a non-compliance rate of 31% characterized by wear of the appliance for less than 2 hours daily a minimum of 68 participants (34 in each group) is required with a power of 80% to detect a minimum difference of 25% in compliance rates at the 0.05 level of statistical significance. To compensate for a dropout rate of at least 10%, the final number to be enrolled in the trial is 84.

For the second part of the study, Initially, 10 one-to-one interviews will be undertaken. Interviews will continue until data saturation has been achieved characterized by a lack of new emergent themes.

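### Intention to treat is promised, but no rule says how exit records or a missing 6-month timer reading enter the primary analysis

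*Combined protocol and SAP*

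**What the plan says.** Trial Objectives sets the primary endpoint: "Objective level of compliance with retainer wear at 6 months (T3) of orthodontic retention". Wear at T2 (3 months) and T4 (12 months) is secondary.

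Study Design / Plan – Study Visits says that participants who want to leave "may do so at any point without affecting continuing care". On their data, the same section provides for "records taken at the point of withdrawal from the study with data analysis on an intention to treat basis". For missed visits it says: "All patients failing an appointment will be sent another". Study Procedures provides at 3, 6 and 12 months for "collection of records i.e. study models and microsensor readings".

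Sample Size Calculation deals with loss only through enrolment: "To compensate for a dropout rate of at least 10%, the final number to be enrolled in the trial is 84".

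Statistical Methods, repeated in the Synopsis, plans to compare duration of wear between groups. It names one comparative model for the main outcome: linear regression, conditional on normality, adjusted for pre-treatment crowding, age and gender. Neither section mentions imputation, carrying a reading forward, a repeated-measures model, an analysis-set definition, visit windows or a sensitivity analysis.

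**The concern.** Intention to treat settles the arm in which a participant is analysed. It does not settle what outcome value a participant has when the 6-month reading was never taken. A single-visit regression of T3 wear needs that value, and the plan does not say where it comes from.

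Two things are at stake. First, this is an adherence trial, so it is plausible that people who leave early are those who wear the retainer least. If such loss differs between arms, leaving them out distorts the comparison, and a larger enrolment does not repair it. Second, with no rule fixed in advance, the handling of early leavers could be chosen after the data are seen. Participants who leave after T3 are not affected.

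**Working it through.** **Inputs from Sample Size Calculation.** Non-compliance 31%, difference 25 points (so 6% in the reminder arm, by subtraction), power 80%, significance level 0.05 (two-sided assumed), 34 per group, at least 10% dropout, 84 enrolled.

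**Assumed inputs.** Equal split (84/2 = 42 per arm), who leaves and in which arm, T2–T3 correlation 0.5 to 0.8, SD of wear 4 to 6 h/day. None of these is in the documents.

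**1. The plan's own figure.** With the unpooled normal formula, n = (z₀.₉₇₅ + z₀.₈₀)² × [p₁(1−p₁) + p₂(1−p₂)] / d² = (1.960 + 0.842)² × (0.2139 + 0.0564) / 0.25² ≈ 33.9, so 34 per group and 68 in total. This reproduces the plan. For 10% loss, 68/0.90 = 75.6, so 76. Enrolling 84 leaves room for 1 − 68/84 = 19% loss, which is compatible with the stated dropout. The numbers are not in dispute.

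**2. What the regression does.** Each participant contributes one T3 value plus arm and covariates. Without a T3 value there is no row. An exit reading, the T2 reading or an imputed value could fill the gap, but the plan selects none of them.

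**3. Error from leaving people out.** In one arm, the error in the completers' mean is m × (mean T3 wear of stayers − mean T3 wear of leavers), where m is the fraction lost. The error in the arm difference is the reminder-arm error minus the control-arm error. With the same m and the same gap in both arms it is zero. With 4 of 42 lost in controls only, m = 4/42 = 0.0952:

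| Assumed gap (h/day) | Shift in control mean (h/day) |
|---|---|
| 2 | 0.19 |
| 6 | 0.57 |
| 12 | 1.14 |

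**4. When leaving depends on T2 wear.** Suppose the 4 controls with the lowest T2 wear lose T3, and there is no true arm difference. Under normality the lowest 4 of 42 average about −1.72 SD, so the other 38 average 4/38 × 1.72 = 0.181 SD too high at T2. Multiplied by the correlation, the T3 error is 0.181 × 0.5 = 0.09 SD to 0.181 × 0.8 = 0.145 SD. Simulation (20,000 runs, 42 per arm) agrees: the completers' difference is off by about −0.09 SD and −0.15 SD, so the benefit of reminders is understated in this scenario. At SDs of 4 and 6 h/day that is roughly 0.09 × 4 = 0.36 to 0.145 × 6 = 0.87 h/day. Using T2 to inform T3 leaves at most 0.003 SD, or 0.003 × 6 = 0.018 h/day.

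**5. Span of results without a rule, on the sample-size scale.** Take 8 lost per arm (the 19% that 84 allows), with 31% and 6% non-compliance in the 34 observed per arm, i.e. 10.54 and 2.04 participants. If missing controls are counted compliant and missing reminder participants non-compliant, the difference is (10.54 − 10.04)/42 = 1.2 points. The reverse gives (18.54 − 2.04)/42 = 39.3 points. These are bounds, not expectations.

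**The case against.** The strongest reply is that exit records and intention to treat stand in the same sentence of Study Visits, so the natural reading is that exit records are collected to keep leavers in the analysis. A reader might infer that the plan, followed as written, is a completers' analysis. The documents do not support that. Omission is the likely default of an ordinary T3 regression, not a stated intention, and the regression itself is conditional on normality. What remains is that exit records supply data but no rule, and someone who simply stops attending may have no exit record. Rebooking does not reach those who withdraw.

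A reader might also infer that the result will be biased, or biased in a known direction. That is not supported either. The illustrations put all loss in one arm, and identical loss in both would leave the difference unbiased. The same example cannot simply be mirrored in the reminder arm on the planned rates, because 6% of 42 is only about 2.5 non-compliers. The simulation favours the T2-based remedy by construction: leaving depends on T2 and every leaver has a T2 reading.

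It is fair, too, that an exit reading before month 6 deserves a place in the analysis. The wear instruction is "on a full-time basis for 6 months, followed by night-time wear for a further 6 months", so such a reading falls under the same instruction as T3. The fix should use it. The participant-flow figure is not visible in the text, and nothing is inferred from it.

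**Conclusion.** The point holds as a gap in the rule, not as an error in a figure and not as proof that data will be missing. Intention to treat is promised, the endpoint is tied to one visit, and the plan does not say how exit records or a missing T3 value enter the only named model.

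The number lost before T3 and the size and direction of any bias cannot be derived from the documents. Under the assumed one-arm loss of 4 in 42, the completers' difference is off by about 0.09 to 0.15 SD. That rests on normal wear, a T2–T3 correlation of 0.5 to 0.8 and leaving that depends on T2. The concern needs loss that is related to wear and differs between arms. It is worth acting on because the readings that would reduce the problem are already planned.

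**What to change.** Before data are seen, make the primary wear-duration analysis one of the following:

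- a linear mixed model of timer wear at T2, T3 and T4 with arm, visit, arm × visit, pre-treatment crowding, age and gender, taking the T3 arm difference as the primary estimate. An unstructured covariance is sensible because the wear instruction changes after month 6; or
- multiple imputation of T3 wear from T2, any exit reading and the covariates, followed by the regression already named.

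Also state:

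- how exit readings are used: as an auxiliary variable in the imputation, or assigned to the nearest visit by a pre-set window;
- a fallback if wear is clearly non-normal, such as bootstrap intervals, since neither option removes the normality condition in Statistical Methods;
- one sensitivity analysis in all randomised participants, with missing T3 wear set to a pre-stated unfavourable value in both arms (zero for those with no reading). Label it an extreme scenario, because leaving the trial does not mean that wear stops.

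The fix concerns the duration analysis in Statistical Methods. It does not settle how that relates to the compliance-rate scale used for sample size.

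The cost is slightly more analysis work, with no new visits or data. The primary analysis would rest on a missing-at-random assumption, which the sensitivity analysis probes but cannot test. Participants with no reading contribute little or nothing to the primary estimate.

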### **Study Scheme Diagram**

To reinforce the above and which demonstrates the life cycle of the study in a schematic form (see example below)

Please refer to figure 1.

[figure not shown]

Figure 1. CONSORT chart showing the flow of participants through each stage of the trial

## STUDY PROCEDURES

Participants will be recruited by treating clinicians at Institute of Dentistry, Barts and The London School of Medicine and Dentistry. Potentially eligible participants will be given an information sheet detailing the study and its objectives at the visit prior to removal of their fixed appliances. Participants agreeing to be involved will be asked to sign a consent form for inclusion in the study at the following visit. Patients under 16-18 years can consent for themselves only if they were deemed mature to make a decision, this will be decided by the CI and PI. Otherwise, the parent will be asked to consent for their child.

Following removal of the appliances, consenting participants will be randomly allocated to one of two groups by computer-generated random allocation. Allocation will be concealed from the treating clinician using of an opaque sealed envelope system. Standard orthodontic study models will be available for all participants following removal of the appliances (T1).

Participants will then be reviewed at 3, 6 and 12 months for regular retainer checks and collection of records i.e. study models and microsensor readings.

One-to-one interviews will be undertaken in a confidential non-clinical areas. Interviews will continue until data saturation has been achieved characterized by a lack of new emergent themes.

All documents including models will be securely held in a locked office, photos will also be stored on an encrypted trust computer.

### Schedule of Assessment (in Diagrammatic Format)

Please use a table format to detail the schedule of assessments that the participant will undergo at each visit (see example below).

Assessment	Randomization	Retention phase	Treatment phase	End of Study	Follow up visits
Enrollment, written information sheet, consent	Computer-generated random allocation. Allocation will be concealed from the treating clinician using of an opaque	3-monthly retainer check visits and records collation (study models and timer readings)	One-to-one interview with subset of recruited participants	End of retainer check visits	24 months

	sealed envelope system				
--	------------------------	--	--	--	--

### **End of Study Definition**

Follow-up of retention procedures will be undertaken over a 24-month period. The final retainer checks will be undertaken at 12 and 24 months in keeping with standard orthodontic practice. The study will be completed following the 24-month visit.

## STATISTICAL CONSIDERATIONS

### **Summary**

The study compares compliance levels in two groups. Only group one will receive an electronic reminder. The research question is therefore summarised as “does electronic reminders improve compliance levels with orthodontic retainers”.

The research question is expressed as the following set of hypotheses:

**Null hypothesis:** *Periodic, tailored electronic reminders are ineffective in improving compliance with orthodontic retention.*

**Alternative Hypothesis:** *Periodic, tailored electronic reminders are effective in improving compliance with orthodontic retention.*

### Sample Size Calculation

Based on previous research (Tsimos et al., 2014) alluding to a non-compliance rate of 31% characterized by wear of the appliance for less than 2 hours daily a minimum of 68 participants (34 in each group) is required with a power of 80% to detect a minimum difference of 25% in compliance rates at the 0.05 level of statistical significance. To compensate for a dropout rate of at least 10%, the final number to be enrolled in the trial is 84.

For the second part of the study, Initially, 10 one-to-one interviews will be undertaken. Interviews will continue until data saturation has been achieved characterized by a lack of new emergent themes.

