	
software (SPSS, New York, NY, USA). Assessment of the reliability of the measures used in the study will be tested by assessing agreement between the measurements (Bland and Altman, 1986). Baseline characteristics will be summarised to ensure that all groups are similar with respect to potential confounding variables. Inferential statistics will be used to compare differences in the duration of appliance wear between the treatment groups. If the data follows a normal distribution, linear regression analysis will be used to assess the influence of retention protocol on the main outcome. This technique will allow for confounding factors including degree of crowding pre-treatment; age; and gender. The level of statistical significance will be pre-specified at <math>P<0.05</math>.
 
Transcripts of the interviews will be entered in NVivo 10 TM qualitative data analysis software (QSR International) and anonymised for analysis.
 
The Framework approach will be used to analyse the qualitative data (Gale et al., 2013). This approach facilitates the thematic analysis of qualitative data in a structured way around the key questions in the topic guide.

Proposed Start Date	May 2016
Proposed End Date	24 months after recruitment of the final participant.
Study Duration	24 months

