### Statistical Methods

Data analysis will involve descriptive and analytical statistics performed using software (SPSS, New York, NY, USA). Assessment of the reliability of the measures used in the study will be tested by assessing agreement between the measurements (Bland and Altman, 1986). Baseline characteristics will be summarized to ensure that all groups are similar with respect to potential confounding variables. Inferential statistics will be used to compare differences in

the duration of appliance wear between the treatment groups. If the data follows a normal distribution, linear regression analysis will be used to assess the influence of retention protocol on the main outcome. This technique will allow for confounding factors including degree of crowding pre-treatment; age; and gender. The level of statistical significance will be pre-specified at  $P<0.05$ .

For the second part of the study the Framework approach will be used to analyse the qualitative data (Gale *et al.*, 2013). This approach facilitates the thematic analysis of qualitative data in a structured way around the key questions in the topic.

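### The stated 80% power is for a comparison of compliance proportions, but the only variable the plan names for analysis is wear duration

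*Combined protocol and SAP*

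**What the plan says.** - **Sample Size Calculation.** The starting point, taken from previous research, is a "non-compliance rate of 31% characterized by wear of the appliance for less than 2 hours daily". The trial is then given "power of 80% to detect a minimum difference of 25% in compliance rates" with 34 participants in each group. Enrolment is set at 84 to allow for dropout of at least 10%. The rate expected in the reminder group is not stated.
- **Statistical Methodology and Analysis (synopsis), repeated in Statistical Methods.** "Inferential statistics will be used to compare differences in the duration of appliance wear between the treatment groups".
- **Statistical Methods.** "If the data follows a normal distribution, linear regression analysis will be used to assess the influence of retention protocol on the main outcome", adjusted for pre-treatment crowding, age and gender. No method is named for data that are not normal.
- **Trial Objectives, Primary Endpoint.** "Objective level of compliance with retainer wear at 6 months (T3) of orthodontic retention", with no scale and no cut-off.
- **Study Procedures.** Wear is measured through "collection of records i.e. study models and microsensor readings".
- **Study Design / Plan – Study Visits.** All participants are told to "wear vacuum-formed (Essix-type) retainers on a full-time basis for 6 months", then to wear them at night for a further 6 months.

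**The concern.** The sample size is built on a yes/no variable. The analysis text is built on a continuous one. Power belongs to a particular variable, effect and test, so a figure worked out for a difference in rates does not carry over to a difference in mean hours unless something links the two. The primary endpoint does not supply that link, because its wording fits either scale.

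Two things are at stake. First, a null result on duration could not be read as having had 80% power for a 25% difference, and readers cannot tell what difference in hours the trial was able to detect. Second, because the primary variable and its test are not pinned down in one place, the choice between hours and a rate could be made after the timers are read.

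**Working it through.** **Inputs from the documents.** Non-compliance 31%; difference 25%; power 80%; significance level 0.05 (sidedness not stated, two-sided used here); 34 per arm; 84 enrolled; dropout at least 10%. All are in Sample Size Calculation. No SD of wear and no target difference in hours appears anywhere.

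**Step 1: reproduce the 34.** Read the 25% as absolute points, so non-compliance falls from 31% to 6% (the 6% is inferred). With unpooled variance:

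n per arm = (1.960 + 0.842)² × [p₁(1 − p₁) + p₂(1 − p₂)] / (p₁ − p₂)²

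= 7.849 × (0.31 × 0.69 + 0.06 × 0.94) / 0.25² = 7.849 × 0.2703 / 0.0625 = 33.94, rounded up to 34.

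The same formula under other readings:

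| Reading of the 25% | n per arm |
|---|---|
| 31% vs 6% (absolute fall in non-compliance) | 33.94 |
| 31% vs 56% | 57.8 |
| Compliance 69% vs 86.25% (relative rise) | 87.7 |
| Non-compliance 31% vs 23.25% (relative fall) | 512.7 |

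Of the readings tried, only the first gives 34. The stated power is for a comparison of proportions, and the arithmetic behind it is sound. (Pooled variance gives 36.67, so 37.)

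**Step 2: power of the sized comparison.** 84 × 0.9 = 75.6, or about 38 per arm after 10% dropout. Exact binomial enumeration at 31% vs 6%:

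| Test | 34 per arm | 38 per arm |
|---|---|---|
| Chi-square, uncorrected | 80.6% | 84.7% |
| Fisher's exact | 69.8% | 76.9% |

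The actual size of the chi-square test at 34 per arm is 5.23% if the common rate is 18.5% and 5.45% if it is 31%.

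**Step 3: what 34 per arm means for duration.** By the normal approximation, the detectable difference at 80% power is (1.960 + 0.842) × √(2/34) = 0.68 SD. The two-sample t calculation gives 0.69 SD at 34 per arm and 0.65 SD at 38. To put this in hours an SD must be assumed, since the documents give none: with 3 h/day, 0.69 × 3 = 2.1 h/day; with 6 h/day, 0.69 × 6 = 4.1 h/day.

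**Step 4: can the 31% vs 6% be converted into power for duration?** Not from the documents. If hours were normal with equal SDs, the two rates would imply a shift of z(0.94) − z(0.69) = 1.06 SD, and power at 34 per arm would be 99%. If wear were instead an assumed mixture, in which reminders only move people across 2 h/day and those already above it gain nothing, simulated power is 40% to 73%, depending on the assumed spread. Neither model comes from the plan. They show only that the answer depends on information the plan does not contain.

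**The case against.** The strongest reply is that the plan is loosely worded rather than contradictory. The phrase about inferential statistics names no test, regression is conditional on normality, the main outcome is not defined, and the endpoint speaks of a level of compliance. A test of proportions could sit within that wording. This stands: such a test is not expressly excluded, and it would be too strong to say the plan rules it out. But duration is the only variable those sentences name, so the power statement still has no named analysis attached to it.

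A second reply is that analysing hours usually gains power over splitting them at a cut-off, and that enrolling 84 leaves slack. A reader might infer from the mismatch that the trial is underpowered. The documents do not support that: with no SD and no target difference, power for duration could be above or below 80%. Equally, the extra enrolment does not turn a figure for rates into a figure for hours.

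A third point concerns the 2-hour threshold. A reader might infer that someone wearing the retainer for 3 hours a day at 6 months would count as compliant in this trial, despite the full-time instruction. The plan does not say so. It attaches the threshold to a rate from previous research and states no compliance cut-off of its own. The conflict with the wear instruction arises only if that threshold is meant to apply at T3.

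Finally, a confidence interval for duration would show the precision achieved whatever the sample size section says. That is true, and it limits the harm, but it does not correct the only power statement in the plan.

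**Conclusion.** The mismatch is real. The 80% at 34 per arm is for 31% vs 6% non-compliance; the 6% and the two-sided test are inferred, but the match at 33.94 is close and the alternatives are far off. The analysis text names duration, for which 34 per arm gives 80% power at 0.69 SD and 38 per arm at 0.65 SD, assuming a two-sided 0.05 two-sample t comparison with equal SDs. The stated power is therefore not a property of the analysis as written.

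This is not an arithmetic error, and neither a loss of power nor a bias has been shown. The point should be fixed, and fixed before the timer data are read; it does not by itself call the trial's size into question.

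**What to change.** Make the Primary Endpoint, Sample Size Calculation and Statistical Methods (with the matching synopsis text) name the same T3 variable, and attach the power statement to its test. Either route is acceptable.

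**A. Keep duration as primary.** Restate the power as 80% for a 0.69 SD difference at 34 per arm (0.65 SD at 38). Describe this as the difference detectable at the planned size, not as a justification of that size. Give the assumed SD and its source when available, and report the proportion as a named secondary. *Cost:* a less favourable power statement, and an SD that the sponsor must source; until then, whether 0.69 SD is worth detecting cannot be judged.

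**B. Make the proportion primary.** State both rates (31% and 6%) in Sample Size Calculation. In Statistical Methods, name an unadjusted chi-square test with the risk difference and its 95% confidence interval. The test should be named because Fisher's exact test, which the plan does not propose, would fall short of 80% at both 34 and 38 per arm. Keep the adjusted duration analysis as a named secondary: only 34 × (0.31 + 0.06) = 12.6 to 38 × 0.37 = 14.1 non-compliers are expected in total, few for a covariate-adjusted model of the proportion. *Cost:* information on hours above the cut-off is discarded, and the test's actual size is about 5.2% to 5.5% at 34 per arm.

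Under either route, say whether the under-2-hours definition is to be applied to this trial's participants. If it is, reconcile it with the full-time wear instruction that runs up to T3. These are wording changes and need no extra participants.

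### Does an enrolment target of 84 contradict a requirement of 68 evaluable participants and a 10% dropout allowance?

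*Combined protocol and SAP*

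**What the plan says.** All the relevant text is in the Sample Size Calculation section of the combined protocol and SAP. The starting point is "a non-compliance rate of 31% characterized by wear of the appliance for less than 2 hours daily", and the aim is "to detect a minimum difference of 25% in compliance rates". On that basis the plan says "a minimum of 68 participants (34 in each group) is required with a power of 80"%, at the 0.05 level. It then sets recruitment: "To compensate for a dropout rate of at least 10%, the final number to be enrolled in the trial is 84".

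The section gives no inflation formula and no other dropout figure. The synopsis only refers back to the sample size calculation for the number of participants, so nothing elsewhere fills the gap.

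**The concern.** A statistician checking the sentence divides 68 by 0.90 and gets 76, not 84. Working backwards, 84 corresponds to a loss of about 19%, nearly twice the only percentage printed. A round 20% does not give 84 either, since 68/0.80 = 85. It is natural to suspect that the base number, the dropout rate or the target has been misreported.

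If so, two things could suffer. Readers would not know what level of attrition the trial was built to absorb, so a loss of 15%, say, might be reported as a shortfall when it is not. And the 80% power might not describe the trial actually being run.

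**Working it through.** **Inputs.** All come from the Sample Size Calculation section: 68 evaluable (34 per group), dropout of 10% or more, 84 to be enrolled, control non-compliance 31%, difference 25%, power 80%, significance level 0.05. Three readings are assumptions: equal allocation (implied by 34 in each group), a two-sided test (sidedness is not stated), and 25% as an absolute difference, so that compliance goes from 69% to 94% and non-compliance from 31% to 6%.

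**Step 1: is 68 sound on the plan's own inputs?** With unpooled variances,

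n per arm = (1.960 + 0.842)² × [0.31 × 0.69 + 0.06 × 0.94] / 0.25² = 7.849 × 0.2703 / 0.0625 = 33.94, so 34 per arm and 68 in total.

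The arcsine formula gives 33.35, again 34 per arm. The stated 68 is therefore reproduced.

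**Step 2: what does exactly 10% dropout require?**

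- Dividing by the retained fraction: 68/0.90 = 75.6, so 76 (38 per arm).
- The cruder multiplication: 68 × 1.10 = 74.8, so 75.

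Neither gives 84.

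**Step 3: what loss does 84 cover?** 84 − 68 = 16, and 16/84 = 19.0%. With 42 per arm, each arm can lose 8 and still have 34.

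| Dropout | 68/(1 − dropout) | Covered by 84? |
|---|---|---|
| 10% | 75.6 | yes |
| 15% | 80.0 | yes |
| 19% | 83.95 | yes |
| 20% | 85.0 | no, short by 1 |

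**Step 4: do the three statements conflict?** A dropout rate with 10% as its floor sets a minimum enrolment of 76. A target of 84 meets that minimum with 8 to spare. Any planned rate from 10% to 19% satisfies both the wording and the target. A conflict would exist only if the plan had fixed dropout at 10%, which it does not.

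**Step 5: effect on power.** At 10% loss, 84 × 0.90 = 75.6 remain, about 38 per arm. On the unpooled basis that reproduces 68, power is 80.1% at 34 per arm and 84.2% at 38. On the pooled basis it is 76.8% and 81.4%. Whichever convention is chosen, the surplus raises power. The two conventions should not be mixed: setting the pooled 81.4% beside the stated 80% understates the gain.

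**The case for a change.** The strongest argument for a change is that a floor cannot by itself produce a number. Some specific rate or base must have led to 84, and the plan does not disclose it. There is also a rival route. The pooled formula gives 36.67, so 37 per arm (74 in total), and 37/0.90 = 41.1, so 42 per arm and exactly 84. If that was the calculation, the trial needs 74 completers, not 68, for 80% power (80.4% at 37 per arm, pooled). A 15% loss would leave 84 × 0.85 = 71.4, above one benchmark and below the other.

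Part of this stands: the step from 68 to 84 cannot be reproduced from the text. The rest does not carry far. The plan names its benchmark outright as "a minimum of 68 participants (34 in each group) is required", and 74 appears nowhere in it. The rival route shows that the origin of 84 cannot be inferred; it does not show that 68 is wrong. The difference between 68 and 74 comes from the choice of variance formula for the base number, not from the dropout step, and a larger enrolment helps under either.

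Nor does the plan tie any action to the dropout percentage. It describes no interim look and no sample size re-estimation, and the Trial Committees section states that there are no committees. A reader judging whether power was kept would count completers against 68. Cutting the target to 76 so that the division comes out exactly would give up the margin of 8 in a trial with endpoints at 6 and 12 months, for no statistical benefit.

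**Conclusion.** The division behind the concern is correct: 76 at exactly 10% loss, against 84 stated, with 84 covering losses up to 19.0%. The inference that a planning figure is wrong does not follow. The figures 68, a floor of 10% and 84 are mutually consistent, the 68 is reproduced from the stated inputs, and the discrepancy lies on the safe side. Following the plan as written costs no power and alters no result or decision.

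What remains is an unstated allowance. A one-line note that 84 (42 per arm) keeps 68 evaluable with up to 19% loss would be a courtesy to readers, not a correction.

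The dropout arithmetic rests only on 68 and 84, plus equal allocation and roughly even losses for the figure of 34 per arm. The power figures also assume a two-sided test and an absolute difference of 25 percentage points, 69% against 94%.
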